4.2 METHOD OF TREATMENT ASSIGNMENT

This is a Phase Ib/II, open-label, multicenter, non-randomized, dose-escalation study of Atezo+G+Len in patients with relapsed or refractory FL. During the dose-escalation phase, an interactive voice or web-based response system (IxRS) will be used to assign patients to dosing groups that vary according to the dose of lenalidomide given during induction treatment. During the expansion phase, patients will receive lenalidomide at the RP2D during induction treatment. All patients will receive lenalidomide at a dose of 10 mg during maintenance treatment. Atezolizumab and obinutuzumab will be given at stable doses to all patients, during both induction and maintenance treatment.

Enrollment tracking will be performed through use of the IxRS. Prior to initiating screening, the study site should confirm via the IxRS that slots are available for enrollment. After written informed consent has been obtained and preliminary eligibility has been established, the study site will submit documentation supporting eligibility to the Sponsor and obtain the Sponsor's approval to enroll the patient. Once the Sponsor reviews and approves the patient for enrollment, the patient number will be assigned and the patient will be enrolled via the IxRS. The Sponsor will communicate to the sites impending closure of screening.

4.3 STUDY TREATMENT

4.3.1 Formulation, Packaging, and Handling

4.3.1.1 Obinutuzumab

Obinutuzumab will be supplied by the Sponsor as an investigational medicinal product (IMP). Obinutuzumab will be provided as a single-dose, sterile liquid formulation in a 50-mL glass vial containing 1000 mg/40 mL of obinutuzumab. In addition to the drug substance, the liquid is also composed of histidine, trehalose, and poloxamer 188. For information on the formulation and handling of obinutuzumab, see the obinutuzumab Investigator's Brochure and the Pharmacy Manual.

4.3.1.2 Atezolizumab

Atezolizumab will be supplied by the Sponsor as an IMP. Atezolizumab drug product is formulated as 60 mg/mL of atezolizumab in 20 mM histidine acetate, 120 mM sucrose, pH 5.8 with 0.04% (w/v) polysorbate 20. Atezolizumab is provided in a single-use, 20-mL USP/Ph. Eur. Type 1 glass vial as a colorless to slightly yellow, sterile, preservative-free clear liquid solution intended for IV administration. The vial is designed to deliver 20 mL (1200 mg) of atezolizumab solution but may contain more than the stated volume to enable delivery of the entire 20-mL volume. Extraction of 14 mL of atezolizumab solution will contain an 840-mg dose. For information on the formulation and handling of atezolizumab, see the Atezolizumab Investigator's Brochure and the Pharmacy Manual.

4.3.1.3 Lenalidomide

Lenalidomide will be supplied by the Sponsor as an IMP. Lenalidomide will be provided as 5-, 10-, 15-, and 20-mg capsules.

Female caretakers of patients taking lenalidomide who are of childbearing potential should not handle or administer lenalidomide unless they are wearing gloves. Lenalidomide should be stored at room temperature away from direct sunlight and should be protected from excessive heat and cold.

For information on the formulation and handling of lenalidomide, see the local prescribing information for lenalidomide.

4.3.2 Dosage, Administration, and Compliance

The treatment regimens are summarized in [Table 4](#) and [Table 5](#) (see Sections [4.3.2.4](#) and [4.3.2.5](#)).

Premedication and treatment for TE prophylaxis should be administered as described in Section [4.3.2.6](#).

Any overdose or incorrect administration of any of the study treatments should be noted on the Study Drug Administration electronic Case Report Form (eCRF). Adverse events associated with an overdose or incorrect administration of any of the study treatments should be recorded on the Adverse Event eCRF.

4.3.2.1 Obinutuzumab

[figure not shown]
Obinutuzumab will be administered by IV infusion at an absolute (flat) dose of 1000 mg on Days 1, 8, and 15 of the first cycle and on Day 1 of each subsequent cycle during induction treatment, and on Day 1 of every other month (i.e., every 2 months) during maintenance treatment.

Obinutuzumab should be administered as an IV infusion through a dedicated line in an environment in which full resuscitation facilities are immediately available and under the close supervision of an experienced physician. Obinutuzumab infusions will be administered per the instructions outlined in [Figure 2](#) and [Figure 3](#). For patients with bulky lymphadenopathy, the infusion may be given slowly over a longer period of time, or the dose may be split and given over more than 1 day.

No dose modification for obinutuzumab is allowed. Guidelines for treatment delays or discontinuation are provided in [Section 5.1](#).

Premedication with a corticosteroid, analgesic/antipyretic, and antihistamine, as outlined in [Section 4.3.2.6](#) (see [Table 6](#)), is required to reduce the incidence and severity of IRRs. For anaphylaxis precautions, see [Appendix 7](#).

Figure 2 Guidelines for Obinutuzumab Infusions: First Infusion

[figure not shown]

IRR=infusion-related reaction.

^a All patients should receive full premedication with an oral corticosteroid, oral analgesic/anti-pyretic, and antihistamine prior to the first obinutuzumab infusion. Refer to Section 4.3.2.6 for details.

^b Supportive treatment should include acetaminophen/paracetamol and an antihistamine such as diphenhydramine, if not administered within the previous 4 hours. Intravenous saline may be indicated. For bronchospasm, urticaria, or dyspnea, patients may require antihistamines, oxygen, corticosteroids (e.g., 100 mg oral prednisone or equivalent), and/or bronchodilators. For anaphylaxis precautions, see Appendix 7.

Figure 3 Guidelines for Obinutuzumab Infusions: Second and Subsequent Infusions

IRR=infusion-related reaction.

^a Patients should receive full premedication with an oral corticosteroid, oral analgesic/anti-pyretic, and antihistamine prior to the obinutuzumab infusion. Refer to Section 4.3.2.6 for details. In the case of a recurrent Grade 3 IRR, obinutuzumab may be discontinued at the discretion of the investigator, following an individual benefit-risk assessment.

^b Patients who experience wheezing, urticaria, or other symptoms of anaphylaxis must receive full premedication prior to all subsequent doses.

4.3.2.2 Atezolizumab

Atezolizumab will be administered at a flat dose consisting of one of the following:

a) 840 mg Q2W (840 mg on Days 1 and 15 of Cycles 2–6, given in 28-day cycles as induction treatment) and b) 1680 mg Q4W (840 mg on Days 1 and 2 of each month, given as maintenance treatment). Detailed atezolizumab dosing regimens are provided in [Table 4](#) for induction treatment and in [Table 5](#) for maintenance treatment (see Sections [4.3.2.4](#) and [4.3.2.5](#)).

Atezolizumab infusions will be administered as follows:

- The initial dose of atezolizumab will be delivered over 60 (\pm 15) minutes. If the first infusion is tolerated without infusion-associated adverse events, the second infusion may be delivered over 30 (\pm 10) minutes. If the 30-minute infusion is well tolerated, all subsequent infusions may be delivered over 30 (\pm 10) minutes.
- In the event that a patient experiences a mild (NCI CTCAE Grade 1) IRR, the infusion rate should be reduced to half the rate being given at the time of event onset. Once the event has resolved, the investigator should wait for 30 minutes while delivering the infusion at the reduced rate. If tolerated, the infusion rate may then be increased to the original rate.
- In the event that a patient experiences a moderate (NCI CTCAE Grade 2) IRR or flushing, fever, or throat pain, the infusion should be immediately interrupted and the patient should receive aggressive symptomatic treatment. The infusion should be restarted only after the symptoms have adequately resolved. The infusion rate at restart should be half of the infusion rate being given at the time of event onset.
- In the event of a severe or life-threatening (NCI CTCAE Grade 3 or 4) IRR, the infusion should be stopped immediately and aggressive resuscitation and supportive measures should be initiated. In the event of a life-threatening IRR, atezolizumab should be permanently discontinued.

For anaphylaxis precautions, see [Appendix 7](#).

No dose modification for atezolizumab is allowed. Guidelines for treatment delays or discontinuation are provided in Section [5.1](#).

4.3.2.3 Lenalidomide

Lenalidomide will be administered orally once daily on Days 1–21 of Cycles 1–6 (28-day cycles) during induction treatment and on Days 1–21 of each month during maintenance treatment. During the dose-escalation phase, lenalidomide will be administered at a dose of 15 or 20 mg (dose may be de-escalated to 10 mg) during induction treatment and at 10 mg during maintenance treatment. During the expansion phase, lenalidomide will be administered at the RP2D during induction treatment and at 10 mg during maintenance treatment.

Lenalidomide capsules should be swallowed whole with water and should not be broken, chewed, or opened. The capsules may be taken with or without food, except on lenalidomide PK sampling days (see [Appendix 2](#)), when the patient should fast (water allowed) at least 2 hours before and at least 1 hour after the lenalidomide dose. On lenalidomide PK sampling visits, lenalidomide dose will be taken in the clinic.

Lenalidomide should be administered at approximately the same time each day. If a dose of lenalidomide is missed and it has been < 12 hours since the time of the scheduled dose, the patient may take the missed dose. If it has been > 12 hours, the dose should be skipped and the next dose should be taken at the regularly scheduled time. Two doses should not be taken at the same time. If a dose had been vomited, the dose should not be re-taken.

At each cycle, each patient will be supplied with only enough lenalidomide for that cycle. A drug diary will be provided to the patient to record oral administration of doses, including the date and time. Patients will be instructed to return empty bottles or unused capsules. The investigator is responsible for monitoring patient compliance by monitoring the patient diary and counting unused capsules.

4.3.2.4 Induction Treatment with Atezolizumab, Obinutuzumab, and Lenalidomide (Atezo+G+Len)

Patients will receive induction treatment, administered in 28-day cycles as follows:

- Patients will receive six cycles of induction treatment consisting of obinutuzumab and lenalidomide for Cycles 1–6 and atezolizumab for Cycles 2–6 as outlined in [Table 4](#).

Lenalidomide may be administered before or concomitantly with obinutuzumab. After completion of the obinutuzumab infusion, the line will be flushed (unless there is a central line with more than one line/port), after which atezolizumab will be administered.

For patients at increased risk for IRRs (high tumor burden), the obinutuzumab infusion may be split and administered over 2 days, with 100 mg given on Day 1 and 900 mg given on Day 2.

For patients who experience an IRR during obinutuzumab infusion, administration of atezolizumab may be delayed by 1 day if clinically required.

Table 4 Induction Treatment

Treatment	Dose	Route	Regimen (28-Day Cycles)	
			Cycle 1	Cycles 2–6
Lenalidomide	Dose-escalation phase: 15 or 20 mg ^a Expansion phase: RP2D	PO	Days 1–21	Days 1–21
Obinutuzumab	1000 mg	IV	Days 1, 8, and 15	Day 1
Atezolizumab	840 mg	IV	—	Days 1 and 15

IV=intravenous; PO=by mouth; RP2D=recommended Phase II dose.

^a Dose may be de-escalated to 10 mg.

4.3.2.5 Maintenance Treatment with Atezolizumab, Obinutuzumab, and Lenalidomide (Atezo+G+Len)

Patients who achieve a CR, a PR, or stable disease at EOI are eligible for maintenance treatment with atezolizumab and obinutuzumab for 24 months and lenalidomide for 12 months, as outlined in [Table 5](#).

Lenalidomide will be given before other agents are administered on the same day. Obinutuzumab will be administered next, followed by a line flush (unless there is a central line with more than one line/port), after which atezolizumab will be administered.

Maintenance treatment should start 8 weeks (\pm 1 week) after Day 1 of Cycle 6 and will continue until disease progression or unacceptable toxicity for up to 24 months.

Table 5 Maintenance Treatment

Treatment	Dose	Route	Regimen (Months 1–24)
Lenalidomide	10 mg	PO	Days 1–21 of each month for a maximum of 12 months
Obinutuzumab	1000 mg	IV	Day 1 of every other month (i.e., every 2 months), starting with Month 1
Atezolizumab	840 mg	IV	Days 1 and 2 of each month

IV=intravenous; PO=by mouth.

4.3.2.6 Premedication and Other Prophylaxis Treatment

Patients should receive premedication as outlined in [Table 6](#).

Granulocyte colony-stimulating factor (G-CSF) may be administered in each cycle of therapy as primary prophylaxis for neutropenia, per American Society of Clinical Oncology, EORTC, and European Society for Medical Oncology guidelines (Smith et al. 2015) or per each site's institutional standards.

Prophylactic treatment with antibiotics should be administered as per standard practice.

Lenalidomide increases the risk of TE. Anticoagulation prophylaxis should be given after a careful assessment of a patient's underlying risk factors. All patients will receive daily low-dose aspirin (81–100 mg) during lenalidomide treatment and until 28 days after the last dose of lenalidomide. Patients who are unable to tolerate aspirin, who have a history of TE, and who are at high risk of TE should receive warfarin or low-molecular-weight heparin (LMWH).

Table 6 Premedication

Timepoint	Patients Requiring Premedication	Premedication	Administration
Cycle 1, Day 1	
 All patients 	
 Oral corticosteroid ^a 	Administer ≥ 1 hour prior to obinutuzumab infusion
	
 All patients 	
 Oral analgesic/anti-pyretic ^b Antihistamine drug ^c 	Administer ≥ 30 minutes prior to obinutuzumab infusion
	
 Patients at risk for TLS (e.g., because of bulky disease or renal impairment (creatinine clearance < 70 mL/min)) 	
 Allopurinol or suitable alternative such as rasburicase, along with adequate hydration 	Administer prior to obinutuzumab infusion
Cycle 1, Days 8 and 15	
 Patients with Grade 1 or 2 IRR or no IRR during the previous infusion 	
 Antihistamine drug ^b Oral analgesic/anti-pyretic ^c 	Administer at least 30 minutes prior to obinutuzumab infusion
Cycles 2 and beyond, Day 1	
 Patients with Grade 3 IRR, wheezing, urticaria, or other symptoms of anaphylaxis during the previous infusion Patients with bulky disease 	
 Oral corticosteroid ^a 	Administer ≥ 1 hour prior to obinutuzumab infusion
		
 Oral analgesic/anti-pyretic ^b Antihistamine drug ^c 	Administer ≥ 30 minutes prior to obinutuzumab infusion
	
 Patients still at risk for TLS 	
 Allopurinol or suitable alternative such as rasburicase, along with adequate hydration 	Administer prior to obinutuzumab infusion

IRR=infusion-related reaction; TLS=tumor lysis syndrome.

^a Treat with 100 mg of prednisone or prednisolone, 20 mg of dexamethasone, or 80 mg of methylprednisolone. Hydrocortisone should not be used because it has not been effective in reducing rates of IRR.

^b For example, 1000 mg of acetaminophen/paracetamol.

^c For example, 50 mg of diphenhydramine.

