4.6.2 Study Treatment Discontinuation

Study treatment should be permanently discontinued in patients who experience any of the following:

- Anaphylaxis, acute respiratory distress, or Grade 4 IRR
 - If a Grade 3 IRR is recurrent during the second and subsequent cycles, study treatment may be discontinued at the discretion of the investigator, following an individual benefit-risk assessment.
- Life-threatening adverse event
- Grade ≥ 3 non-immune-mediated adverse event that is considered to be related to study treatment and does not resolve to Grade ≤ 2 within 21 days

- Non-immune-*mediated* adverse event that is considered to be treatment related and requires study treatment to be withheld for >21 days
- Immune-*mediated* adverse event that requires atezolizumab to be withheld for >42 days, unless approved by the Medical Monitor
- Any adverse event that meets criteria for permanent discontinuation per guidelines provided in Section 5.1
- Disease progression

Because of the potential for tumor flares with immunotherapies, resulting in early apparent radiographic progression (pseudoprogression/tumor immune infiltration), including the appearance of new lesions followed by delayed response (Wolchok et al. 2009), patients whose CT scans at the end of Cycle 2 meet criteria for disease progression may continue to receive study treatment at the discretion of the investigator and following discussion with the Medical Monitor, if certain criteria are met (see Section 3.1.4 for details). Cases of delayed pseudoprogression have also been described in patients with solid tumors treated with immunotherapies. In case of CT- findings suggestive for pseudoprogression in patients with persistent clinical benefit, the investigator should contact the Medical Monitor to discuss further patient management. Patients who continue to receive study treatment should have a CT scan repeated 4–8 weeks later.

- Pregnancy

In case of toxicity solely attributable to one drug of the combination requiring discontinuation, the other two drugs may be continued for patients experiencing clinical benefit as determined by the investigator after discussion with the Medical Monitor.

The primary reason for study treatment discontinuation should be documented on the appropriate eCRF.

Patients who discontinue study treatment will not be replaced, except as outlined below:

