5.1.1.1 Infusion-Related Reactions and Hypersensitivity Reactions

IRRs have been reported predominantly during the first infusion of obinutuzumab. The incidence and severity of IRRs decreased substantially with the second and subsequent infusions. In the majority of patients, IRRs were mild or moderate and resolved with the slowing or interruption of the infusion and supportive care. The commonly experienced

IRRs have been characterized by hypotension, fever, chills, dyspnea, flushing, nausea, vomiting, hypertension, fatigue, headache, tachycardia, dizziness, diarrhea, and other symptoms.

IRRs may be clinically indistinguishable from IgE-mediated allergic or anaphylactic reactions; anaphylaxis has been reported in patients treated with obinutuzumab.

Hypotension may occur during obinutuzumab IV infusions. Therefore, withholding of anti-hypertensive treatments should be considered for 12 hours prior to and throughout each obinutuzumab infusion and for the first hour after administration. Patients at acute risk of hypertensive crisis should be evaluated for the benefits and risks of withholding their anti-hypertensive medication.

Patients who have preexisting cardiac or pulmonary conditions should be monitored carefully throughout the infusion and the post-infusion period.

Guidelines for medical management of IRRs and anaphylaxis are provided in Section 4.3.2.1 and [Appendix 7](#).

Hypersensitivity reactions with immediate (e.g., anaphylaxis) and delayed (e.g., serum sickness) onset have been reported in patients treated with obinutuzumab. Hypersensitivity reactions typically occur after previous exposure and very rarely with the first infusion. In case a hypersensitivity reaction is suspected during or after an infusion, the infusion should be stopped and treatment permanently discontinued.

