IRRs and anaphylaxis	
 • Guidelines for management of IRRs are provided in Sections 4.3.2.1 (obinutuzumab) and 4.3.2.2 (atezolizumab). • Metamizole (dipyrone) is prohibited in treating atezolizumab-associated IRRs because of its potential for causing agranulocytosis. • In case of anaphylaxis, study treatment should be permanently discontinued.
Renal toxicity	
 • Adjust the dose of lenalidomide^a as outlined below: 
 – If creatinine clearance is ≥ 30 but < 60 mL/min, lenalidomide should be given at a dose of 10 mg/day. – If creatinine clearance is < 30 mL/min and dialysis is not required, lenalidomide should be given at a dose of 10 mg every other day. – If creatinine clearance is < 30 mL/min and dialysis is required, lenalidomide should be given at a dose of 5 mg/day. On dialysis days, the dose should be administered after dialysis.

Table 11 Guidelines for Management of Non-Hematologic Toxicities (cont.)

	Event	Action to Be Taken
TLS	Clinical TLS ^b	
 • Withhold study treatment. • Correct electrolyte abnormalities, monitor renal function and fluid balance, and administer supportive care, including dialysis as indicated. Rasburicase therapy (if approved by the local health authority) may be administered as needed to reduce hyperuricemia. • If symptoms resolve completely, resume atezolizumab and obinutuzumab at full dose and resume lenalidomide at a reduced dose^a per guidelines in Section 5.1.5 for current and subsequent cycles. • Perform chemistry panel every other day for the first week after re-initiation of lenalidomide.
	Laboratory TLS ^b	
 • Withhold study treatment. • Correct electrolyte abnormalities, monitor renal function and fluid balance, and administer supportive care as clinically indicated. • If laboratory abnormalities have resolved completely, resume atezolizumab and obinutuzumab at full dose and resume lenalidomide either at current dose or at a reduced dose^a per guidelines in Section 5.1.5 for current and subsequent cycle, at the investigator's discretion.
Peripheral neuropathy	Grade 4 or Myasthenia gravis (any grade) or Guillain-Barre (any grade)	
 • Permanently discontinue study treatment. • Initiate treatment as per institutional guidelines.

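### The obinutuzumab reaction rules provide for re-treatment after symptoms of anaphylaxis but permanent discontinuation on suspected hypersensitivity, and they disagree on how long full premedication lasts

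*Combined protocol and SAP*

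**What the plan says.** Four places in the protocol deal with what follows a reaction to obinutuzumab.

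- **Section 4.3.2.6, Table 6.** The higher-risk row covers "Patients with Grade 3 IRR, wheezing, urticaria, or other symptoms of anaphylaxis during the previous infusion", plus patients with bulky disease, and lists a corticosteroid, an analgesic/anti-pyretic and an antihistamine. The lower-risk row covers "Patients with Grade 1 or 2 IRR or no IRR during the previous infusion" and lists the antihistamine and analgesic/anti-pyretic without a corticosteroid.
- **Section 4.3.2.1, Figure 3 footnotes.** Footnote b: "Patients who experience wheezing, urticaria, or other symptoms of anaphylaxis must receive full premedication prior to all subsequent doses". Footnote a, on second and later infusions, says: "Patients should receive full premedication with an oral corticosteroid, oral analgesic/anti-pyretic, and antihistamine prior to the obinutuzumab infusion". It does not limit this to higher-risk patients, though it refers to Section 4.3.2.6 for details.
- **Section 5.1.1.1.** "In case a hypersensitivity reaction is suspected during or after an infusion, the infusion should be stopped and treatment permanently discontinued". The same section states: "Hypersensitivity reactions with immediate (e.g., anaphylaxis) and delayed (e.g., serum sickness) onset have been reported in patients treated with obinutuzumab". It also says that IRRs may not be clinically separable from allergic or anaphylactic reactions.
- **Section 4.6.2 and Table 11 (Section 5.1.5.1).** Section 4.6.2 permanently discontinues study treatment for "Anaphylaxis, acute respiratory distress, or Grade 4 IRR". Table 11 says: "In case of anaphylaxis, study treatment should be permanently discontinued".

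**The concern.** A patient who wheezes or develops urticaria during an infusion appears to fall under two sets of instructions. One tells the site how to prepare the next obinutuzumab infusion. The other, once those signs raise suspicion of hypersensitivity, allows no next infusion. Because the protocol says the two kinds of reaction can look alike, the choice is left to whichever section the site consults.

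A second mismatch needs no clinical judgement to see: the two premedication texts use different look-back periods, so a patient with an earlier reaction and a clean infusion since then gets different corticosteroid instructions.

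At stake are contradictory bedside instructions for a potentially serious reaction, at about 15 sites, and uneven conduct between those sites.

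**Working it through.** No formula applies to the inconsistencies themselves, so the passages are set side by side.

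**1. Re-treat or stop**

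| Text | Trigger | Consequence for obinutuzumab |
|---|---|---|
| Table 6, higher-risk row | Symptoms of anaphylaxis at the previous infusion | A further infusion, with full premedication |
| Figure 3 footnote b | The same symptoms | All later doses, with full premedication |
| Section 5.1.1.1 | Suspected hypersensitivity reaction | Permanent discontinuation |
| Section 4.6.2; Table 11 | Anaphylaxis | Permanent discontinuation of study treatment |

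- The first two rows presuppose that obinutuzumab continues. The third rules it out on suspicion alone.
- Section 5.1.1.1 supplies the link between the triggers: it gives anaphylaxis as its example of an immediate hypersensitivity reaction. Symptoms that Table 6 itself describes as those of anaphylaxis can therefore meet the suspicion trigger.
- The Section 5.1.1.1 sentence is an operative rule. Section 4.3.2.1 sends the reader to Section 5.1 for obinutuzumab discontinuation, and Section 4.6.2 adopts the permanent-discontinuation criteria found there. Section 5.1.1.1 in turn sends the reader back to Section 4.3.2.1 and Appendix 7 for managing IRRs and anaphylaxis.
- Appendix 7 covers stopping the infusion, treating and observing. It does not address re-treatment.
- The only visible help in separating the two is timing: Section 5.1.1.1 places IRRs mainly at the first infusion and hypersensitivity typically after earlier exposure. Footnote b belongs to the figure on second and later infusions, which is where hypersensitivity is said to be more typical.
- The Section 4.6.2 option to continue the other two drugs does not settle the matter, because the question is whether obinutuzumab itself continues.

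**2. Look-back for full premedication**

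Take a patient without bulky disease who has urticaria on Cycle 1 Day 1 and no IRR on Day 8. For Day 15:

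- Table 6: the previous infusion was clean, so the lower-risk row applies and no corticosteroid is listed.
- Figure 3 footnote b: full premedication, corticosteroid included.

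Moving the reaction to Day 8, with a clean Day 15, gives the same split at Cycle 2 Day 1. The mismatch therefore does not depend on whether footnote b reaches back to the first infusion. Figure 3 footnote a, read without its cross-reference, would give full premedication at later infusions to every patient, which is a third version.

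**3. Can the number affected be derived?**

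Table 8 gives all-grade IRR rates of 14.8% for obinutuzumab plus lenalidomide and 73% to 75% for obinutuzumab. With 46 planned patients:

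- 46 × 0.148 = 6.8 patients with any IRR
- 46 × 0.73 = 33.6 and 46 × 0.75 = 34.5 patients with any IRR

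The share of these with wheezing, urticaria or other symptoms of anaphylaxis is not given, so these figures do not yield a count of patients who fall under both rules.

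**The case against.** The best answer is that the rules are tiered. Symptoms are not the diagnosis: Figure 2 footnote b offers supportive treatment for bronchospasm, urticaria or dyspnea, Table 6 premedicates after such symptoms, and Section 4.6.2 and Table 11 stop treatment only for anaphylaxis. A physician who judges urticaria to be part of an IRR premedicates; one who diagnoses anaphylaxis stops. This stands for Section 4.6.2 and Table 11. A reader might infer that they flatly contradict Table 6, but they name anaphylaxis, not its symptoms. The answer does not reach Section 5.1.1.1, where suspicion is enough.

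The Figure 2 and 3 flowcharts are the infusion guidelines, and only their footnotes are legible here. They may contain a separating rule, so the finding on re-treatment is limited to the visible text.

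On the look-back, footnote b is worded as an obligation and Table 6 as a recommendation, and full premedication includes everything in the lower-risk row. A site could satisfy both texts by giving the fuller set. That is correct, but a site working from Table 6 alone would have no sign that another text asks for more.

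A reader might also infer that the rule a site follows shifts the CR rate, because a patient stopped before Cycle 2 never receives atezolizumab and so falls outside the primary population (Section 6.2). The documents do not support putting a size on this. Section 5.1.1.1 describes hypersensitivity as very rare at the first infusion. Expansion-phase patients who stop before receiving every component are replaced (Section 4.6.2). An additional analysis of all enrolled patients is planned (Section 6.6.1). The share of IRRs concerned is unknown, and the upper IRR rates are for obinutuzumab rather than for its combination with lenalidomide.

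**Conclusion.** Two inconsistencies stand. Table 6 and Figure 3 footnote b provide for further obinutuzumab after symptoms that can trigger permanent discontinuation under Section 5.1.1.1, and the visible text gives no criterion for choosing between them. Footnote b and Table 6 also use different look-back periods for full premedication, with footnote a adding an unrestricted statement. Section 4.6.2 and Table 11 need aligning for consistency but do not directly contradict Table 6.

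The first part assumes that the Figure 2 and 3 flowcharts do not already resolve it; the second rests on the legible wording alone. The point matters for patient safety and uniform site conduct. The number of patients affected cannot be derived, and no sample size, error rate, power or CR-rate effect is claimed. No view is taken on which clinical rule is right.

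**What to change.** The sponsor should reconcile Table 6, Figure 3 footnotes a and b, Section 5.1.1.1, Section 4.6.2 and the IRR and anaphylaxis row of Table 11, and check them against the Figure 2 and 3 flowcharts. The result should be:

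- each presentation (wheezing or urticaria judged to be an IRR, suspected hypersensitivity, anaphylaxis) leads to exactly one stated outcome, with the basis for telling them apart written down;
- one look-back period for full premedication is used in every place, stating which drug's infusion counts. This is needed because from Cycle 3 the infusion before obinutuzumab on Day 1 is atezolizumab on Day 15 of the previous cycle.

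The clinical content is for the sponsor's safety physicians to set. The cost is a wording change in these passages at the next amendment, with no new procedure or data collection.
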